4. INTRODUCTION

Schizophrenia is a chronic, complex and debilitating mental disorder associated with high morbidity and mortality. Typical onset of schizophrenia is during late adolescence and early adulthood. The disease is characterized by positive symptoms (hallucinations, delusions, and disorganized thoughts), negative symptoms (flat affect, anhedonia, ambivalence, and amotivation), and cognitive deficits (associated with memory, judgement, and executive planning). Individuals living with schizophrenia report worse health-related quality of life and have significantly reduced life expectancy.

Despite intense ongoing research, the outcomes from best practice treatment are often suboptimal. The median proportion of people with schizophrenia who meet clinical and social recovery criteria is only 13.5% ([Charlson, 2018](#)). Antipsychotic drugs that act by blocking dopamine D2 receptors (typical antipsychotics) or both the D2 and serotonin (5-HT₂) receptors (atypical antipsychotics) have been the mainstay of treatment for psychosis and positive symptoms for many years; however, a substantial proportion of patients remain symptomatic ([Lane, 2013](#); [Bugarski, 2016](#)) due to lack of efficacy and/or poor tolerability.

N-methyl-D-aspartate receptor (NMDAR) hypofunction is believed to have an important role in the pathophysiology of schizophrenia ([Balu, 2015](#)). In patients with schizophrenia, D-serine, an endogenous co-agonist for the NMDA receptor, concentrations in the blood, cerebrospinal fluid (CSF), and in postmortem brain tissue have been reported to be lower than normal controls ([Hashimoto, 2003](#); [Hashimoto, 2005](#); [Cho, 2016](#); [Bendikov, 2007](#)). Potentiation of the NMDAR-mediated neurotransmission by glycine site modulators, including D-serine, is considered a novel treatment approach to help improve symptoms of schizophrenia and a number of clinical studies have shown benefit to patients with schizophrenia following treatment with D-serine ([Tsai, 1998](#); [Heresco-Levy, 2005](#); [Lane, 2005](#); [Lane, 2010](#); [Kantrowitz, 2010](#); [Ermilov, 2013](#); [Kantrowitz, 2018](#)). A potential limitation to the development of D-serine as a therapeutic is that it has been shown in preclinical testing to cause nephrotoxicity in rats ([Ganote, 1974](#)). The cause of nephrotoxicity is believed to result from the production of hydrogen peroxide in the kidney by D-amino acid oxidase ([Mothet, 2000](#); [Verrall, 2010](#)).

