CTP-692 is a deuterated analog of D-serine and in nonclinical studies has been shown to have nearly identical binding and functional properties as D-serine at the NMDA receptor. In rats, CTP-692 was found to have greater brain exposure when compared to D-serine. Importantly, in other preclinical investigations in the rat, the renal toxicity of D-serine was demonstrated by dose related increases in serum BUN and creatinine but over the same dose range CTP-692 was found to have no significant increase in these parameters, suggesting the potential for an improved renal safety profile for the compound.

The CTP-692 Investigator's Brochure (IB; [CTP-692 Investigator's Brochure](#), Concert Pharmaceuticals Inc., 2019.) should be consulted for detailed technical information and discussion of previous clinical and non-clinical evaluations.

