The majority of studies with D-serine in patients have used a dose of 30 mg/kg/day, a few have administered 60 mg/kg/day and in one study the highest dose was 120 mg/kg/day. The doses of D-serine in these studies approximated to 2.1 g/day, 4.2 g/day and 8.4 g/day, respectively, for a body weight of about 70 kg. The duration of treatment with D-serine ranged from 1 day (single dose) to 4 weeks of daily treatment with the 120 mg/kg/day dose (Kantrowitz, 2010) and 16 weeks of daily treatment with 60 mg/kg/day (Kantrowitz, 2015). D-serine was well tolerated in almost all subjects across all doses. Kantrowitz (2010) dosed 30 mg/kg/day, 60 mg/kg/day and 120 mg/kg/day as 2 divided daily doses of D-serine for 4 weeks with no safety issues at doses < 120 mg/kg. At the 120 mg/kg dose, 1 of 16 patients showed 2+ proteinuria without glycosuria during the final week of treatment with no significant change in creatinine. The proteinuria resolved following D-serine discontinuation, two patients discontinued for asymptomatic transaminitis which also resolved, and two additional patients withdrew consent for side effects (insomnia after one dose and GI distress). In the Kantrowitz (2015) study that dosed 60 mg/kg/day for 16 weeks, two patients in the D-serine group withdrew from the study due to out of range renal values that were possibly related to study treatment versus none in the placebo group. Trace or greater proteinuria was observed in 17 of 45 individuals in post-screening urinalysis. Of these 17 individuals, 11 were randomly assigned to D-serine and 6 were randomly assigned to placebo. All abnormalities resolved during continued treatment. For other adverse events, 1 of 20 patients in the D-serine group expressed suicidal thoughts at Week 11 and was hospitalized but remained in the study. Two patients of 24 in the placebo group were withdrawn from the study due to conversion to psychosis versus none in the D-serine group. However, one patient in the D-serine group showed psychosis symptoms at the final study visit.

The results described above suggest clinical benefit of D-serine in patients with schizophrenia, however, its full clinical potential may be limited due to preclinical nephrotoxic findings at higher, and potentially more clinically-relevant, doses. Given the improved preclinical profile, CTP-692 has the potential to be an adjunctive treatment of schizophrenia with less renal toxicity risk compared to D-serine.

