4.2. Summary of CTP-692 Clinical Data

The Phase 1 program was designed to assess the safety, tolerability and pharmacokinetic profile of CTP-692 in healthy volunteers. The Phase 1 program included three studies: a crossover comparison of CTP-692 versus D-serine (CP692.1001), a single-ascending dose study that also assessed the effect of food on the pharmacokinetics of CTP-692 (CP692.1002), and a multiple-ascending dose trial assessing CTP-692 dosed orally over seven days (CP692.1003). The total number of healthy subjects exposed to one or more doses of CTP-692 in the three Phase 1 studies conducted to date is 67. The goals of the early clinical development program for CTP-692 were (1) to characterize the single- and multiple-dose plasma pharmacokinetic (PK) profiles of the drug, (2) to evaluate safety and tolerability of the drug following single- and multiple-dose administration and (3) to provide guidance for dose selection in subsequent efficacy studies in patients with schizophrenia. The CTP-692 IB ([CTP-692 Investigator's Brochure](#), Concert Pharmaceuticals Inc., 2019.) should be consulted for information on CP692.1001. The single-ascending dose study (CP692.1002) and multiple-ascending dose study (CP692.1003) are discussed below.

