- Standard 12-lead ECG (Weeks 6 and 12 only; if Week 6 visit is a remote visit, ECG assessment may be performed at Week 8 or 10)
- Urine pregnancy tests for women of childbearing potential
- Alcohol breath test
 - o *Patient may be discontinued if they test positive at any two visits during the treatment period*
- Serum chemistry, hematology, and coagulation parameter evaluations (Weeks 6 and 12 only)
- Serum renal parameters and urinalysis
- Blood sample for assessment of CTP-692 levels (pre-dose if dose of Study Medication is administered in the clinic at Weeks 2, 4, 6, 8, and 10)
 - o *If possible, time of last dose taken should also be recorded*
- Dispensation of Study Medication to take home
 - *A 2-week supply of the Study Medication will be provided at each visit except Week 12*
 - *When study assessments are not conducted in the clinic due to the COVID-19 pandemic, the Study Medication may be sent directly to the patient*
- PANSS (Weeks 2, 4, 8, 10, and 12)
- CGI-S (Weeks 2, 4, 6, 8, 10, and 12)
- C-SSRS (Since Last Visit version)
- PSP (Weeks 6 and Week 12 only)
- SQLS (Week 12 only)
- SAS, AIMS and BARS (Weeks 6 and Week 12 only)
- Blood sample for assessment of CTP-692 levels (post-dose; Week 12 only)
 - *Blood sample should be taken at the end of the visit*
 - *Time of CTP-692 dose and blood draw should be recorded*
- Administration of dose of Study Medication in the clinic with food *at the Week 12 visit*
 - Post Dose blood sample for assessment of CTP-692 levels (Week 12 only)
 - o *Blood sample should be taken at the end of the visit*
 - o *Time of CTP-692 dose and blood draw should be recorded*

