9.3. Patient Withdrawal Criteria

Patients may withdraw from participation in the study at any time. The Investigator may withdraw a patient at any time if they believe the safety of the patient or the integrity of the data are at risk. In addition, patients should be withdrawn if they:

- Experience a serious or intolerable AE
- Develop a clinically significant laboratory or ECG abnormality
- Develop proteinuria of 1-2+ or UACR > 30 mg/g as confirmed by a repeat lab test
- Develop eGFR levels < 60 mL/minute/1.73 m² as confirmed by a repeat lab test
- Develop *symptomatic* ALT or AST elevation ≥ 2 x the ULN on two repeat lab tests or develop *asymptomatic* ALT or AST elevation ≥ 3 x the ULN as confirmed by a repeat lab test
- Develop total bilirubin ≥ 2 x the ULN as confirmed by a repeat lab test
- Exhibit suicidal behavior as determined by an affirmative answer on items 4 or 5 on the C-SSRS
- Do not follow guidelines specified in the protocol (i.e., is noncompliant with protocol procedures or Study Medication administration) or specific instructions by the study staff
- Any medically appropriate reason or significant protocol violation, in the opinion of the Investigator
- Are lost to follow up

In case of two consecutive missed safety assessments due to the COVID-19 pandemic, continued patient participation in the study must be discussed by the Investigator and the Medical Monitor.

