#### **4.5.3 *Laboratory Safety Assessments***

Samples for the following laboratory tests will be collected at the time points specified in the Schedule of Assessments (Table 1).

Alcohol breathalyzer:	Assesses ethyl alcohol
Coagulation:	Includes prothrombin time test (PT), partial prothrombin time test (aPTT), international normalized ratio (INR)
Hematology:	Consists of complete blood count, platelet count, white blood cell count with differential
Pregnancy:	Assesses hCG; conducted for females of childbearing potential only
Serum renal parameters:	Includes blood urea nitrogen (BUN), serum creatinine, eGFR
Serology screen:	Includes human immunodeficiency virus antibody (HIV-Ab), hepatitis B surface antigen (HBsAg), hepatitis C virus antibody (HCV-Ab)
Serum chemistry:	Includes alanine aminotransaminase (ALT; SGPT), albumin (ALB), alkaline phosphatase (ALK-P), amylase, aspartate aminotransaminase (AST; SGOT), total bilirubin, direct bilirubin, indirect bilirubin, calcium (Ca), carbon dioxide (CO 2 ), chloride (Cl), total cholesterol, creatine kinase (CK), follicle-stimulating hormone (FSH), gamma-glutamyl transferase (GGT), glucose, lactic dehydrogenase (LDH), lipase, magnesium, total protein, phosphorus, potassium (K), sodium (Na), uric acid
Urinalysis:	Includes bilirubin, glucose, ketones, nitrates, occult blood, protein, specific gravity, urobilinogen, pH, leukocytes, microscopy, creatinine, UACR, urine volume

Urine drug screen:	Includes amphetamines/methamphetamines, barbiturates, benzodiazepines*, cocaine metabolites, methadone, phencyclidine, opiates
--------------------	--

\* Positive test at Week -5 and Week -3 allowed if drug is prescribed by a physician.

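### Serum ALT, AST and bilirubin are scheduled on treatment only at Weeks 6 and 12, so only the Week 6 result can trigger the Section 9.3 liver limits in time to shorten dosing; adding them to the two-weekly renal draws is a cheap precaution

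*Protocol*

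**What the plan says.** Protocol Section 9.3 lists liver results for which a patient should be withdrawn. Symptomatic ALT or AST counts from 2 x ULN on two repeats. For asymptomatic patients the entry is "ALT or AST elevation ≥ 3 x the ULN as confirmed by a repeat lab test". A further entry reads "Develop total bilirubin ≥ 2 x the ULN as confirmed by a repeat lab test".

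These serum analytes sit in one panel. SAP Section 4.5.3 defines serum chemistry as a list that opens "Includes alanine aminotransaminase (ALT; SGPT), albumin (ALB), alkaline phosphatase (ALK-P), amylase, aspartate aminotransaminase (AST; SGOT), total bilirubin", and protocol Appendix B agrees. The serum renal panel holds only BUN, creatinine and eGFR.

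In the Week 2 to Week 12 list of Section 8.2.2, the chemistry entry reads "Serum chemistry, hematology, and coagulation parameter evaluations (Weeks 6 and 12 only". Serum renal tests and urinalysis carry no week restriction there, so they fall at Weeks 2, 4, 6, 8, 10 and 12. The urinalysis panel includes bilirubin and urobilinogen. A final dose is given in the clinic at Week 12, and the follow-up visit in Section 8.2.3 has no laboratory test.

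On background risk, Section 4 says of D-serine that "it has been shown in preclinical testing to cause nephrotoxicity in rats". Section 4.2 gives the longest CTP-692 dosing so far as "a multiple-ascending dose trial assessing CTP-692 dosed orally over seven days". Section 4.1, on a 4-week D-serine study, reports that "two patients discontinued for asymptomatic transaminitis which also resolved".

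**The concern.** A stopping limit for an asymptomatic rise works only if a test is scheduled. The phone calls in Section 8.2.2.1 ask about adverse events and other medical changes, and the unscheduled visits in Section 11.12 are left to the Investigator. A silent enzyme rise prompts neither.

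Three features make Day 42 a late first check:

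- This is the first trial in the described program to give CTP-692 for more than 7 days.
- The transaminase discontinuations in the cited D-serine study arose within a 4-week course, so by about Day 28.
- Entry allows ALT/AST up to 2 x ULN (exclusion 9), from which a 1.5-fold rise reaches 3 x ULN. Asymptomatic hepatitis C is also allowed (exclusion 18).

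Week 6 is also a single point of failure. If that visit is remote, the ECG may move to Week 8 or 10. No such fallback is written for chemistry, although home or local-laboratory draws reduce the risk.

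At stake is avoidable dosing in a patient who already meets a limit that the sponsor chose.

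**Working it through.** **Inputs**

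- Nominal visit days 14, 28, 42, 56, 70 and 84 (SAP Table 2, written for efficacy windows and used here as nominal days).
- Visit window ±2 days (protocol Table 6).
- Last dose on Day 84 (Section 8.2.2, Week 12).
- T = days from blood draw to confirmed result. The documents state no value, so a range is used.

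**Plan's own count.** Section 8.2.2 gives two post-baseline chemistry tests, on Days 42 and 84. The Day 1 sample is taken before dosing.

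**Tests able to shorten dosing.** The condition is test day + T < 84.

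- Current: 42 + T < 84 holds for T < 42, so 1 test.
- With tests on all six days: 70 + T < 84 holds for T < 14, so 5 tests. For T = 14 to 27 the Day 70 test drops out and 56 + T < 84 still holds, so 4 tests.
- With the ±2-day windows, the Week 10 to Week 12 interval runs from 82 − 72 = 10 to 86 − 68 = 18 days, so the cut-off for the Week 10 test moves within that range.

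**First test and longest gap.** The first test moves from Day 42 to Day 14. The longest gap falls from 84 − 42 = 42 days to 14 days (46 and 18 with the windows).

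**Dosing days avoided (illustrative).** Assume that a rise begins in the stated window and persists. Days avoided = min(84, next current test + T) − min(84, next proposed test + T).

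| Onset (days) | T = 7 | T = 14 |
|---|---|---|
| 1–14 | 49 − 21 = 28 | 56 − 28 = 28 |
| 15–28 | 49 − 35 = 14 | 56 − 42 = 14 |
| 29–42 | 0 | 0 |
| 43–56 | 84 − 63 = 21 | 84 − 70 = 14 |
| 57–70 | 84 − 77 = 7 | 0 |
| 71–84 | 0 | 0 |

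Dosing is shortened in four of six windows for T = 7 and in three for T = 14. No average is given, because the documents supply no distribution of onset times.

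**Volume of extra work**

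- Reports: 4 visits x 240 completers = 960, to 4 x 300 randomized = 1,200. Values: x 3 = 2,880 to 3,600.
- Out-of-range values to classify (Section 11.5), assuming 2.5% to 10%: 0.025 x 2,880 = 72 to 0.10 x 3,600 = 360. Over 22 sites that is about 3 to 16 per site.
- Reports reaching a 9.3 limit by chance, assuming 0.1% to 1%: 960 x 0.001 ≈ 1 to 1,200 x 0.01 = 12.

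**Effect on power.** For a two-sided t-test with difference 5.2, SD 10 and alpha 0.05, 60 per arm gives 80.6%, which reproduces the plan's figure of at least 80%. If all 12 chance cases were confirmed and withdrawn, that is 12/4 = 3 per arm. At 57 per arm power is 78.6%; at 59 it is 80.0%.

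**The case against.** The schedule is visibly risk-based: frequent renal tests for the identified kidney hazard, and mid- and end-treatment checks for the rest. Section 9.3 sets thresholds, not a testing frequency. It also lists ECG abnormalities, and ECGs too are done at Weeks 6 and 12 only.

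Urinalysis at every visit from Week 2 already gives a two-weekly indicator of bilirubin, and Section 11.5 requires clinically significant results to be investigated and repeated.

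The liver signal is thin. The two reversible D-serine cases are reported in the context of 120 mg/kg/day, about 8.4 g/day or 2.1 times the top dose here (8.4/4), and lower doses in that study are described as free of safety problems. Section 4.1 also describes 16 weeks of D-serine at 60 mg/kg/day (about 4.2 g/day) and mentions no liver finding. The Phase 1 studies summarized in Sections 4.2.1 and 4.2.2 report no other clinically significant laboratory findings. The Investigator's Brochure, which "should be consulted for detailed technical information and discussion of previous clinical and non-clinical evaluations", may settle the matter and is not among these documents.

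Much of this stands, and it limits the point to a precaution. It does not close the gap. Urine bilirubin is not a Section 9.3 analyte and does not show an isolated ALT/AST rise. The 16-week study was in people at clinical high risk, not patients with established schizophrenia, and its summary is not proof of liver safety. Unlike an ECG, the extra analytes can use a blood draw that already takes place.

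A reader might infer that the plan leaves the liver unmonitored apart from Week 6, or that Section 9.3 contradicts the schedule. The urinalysis rules out the first, and the absence of any stated frequency in Section 9.3 rules out the second. Nor do the two D-serine cases support an expectation of liver injury with CTP-692.

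**Conclusion.** The point holds as an optional improvement. One scheduled serum result, at Week 6, can trigger the ALT/AST and bilirubin limits in time to shorten dosing. The uncovered case is mainly a silent ALT/AST rise without bilirubin in the urine.

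The visit counts and day gaps follow from the documents. The choice between 5 and 4 useful tests depends on the unstated confirmation time. The dosing-days table also assumes a persistent rise and is illustrative only. No event rate is given, so the number of patients who would benefit is unknown. Clean nonclinical liver data in the Investigator's Brochure would weaken the case.

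**What to change.** In protocol Table 6, protocol Section 8.2.2 and SAP Table 1, add ALT, AST and total bilirubin at Weeks 2, 4, 8 and 10, taken from the existing renal blood draws. Leave the Section 9.3 limits as they are. SAP Section 5.5.3 already summarizes laboratory values at each time point, so no new method is needed; the by-arm liver summaries would have six post-baseline time points instead of two. Before adopting the change, check the liver data in the Investigator's Brochure and confirm that sample volume and handling suit the extra analytes.

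The change needs a protocol amendment with IRB approval before sites act on it (Section 14.4), and probably eCRF and Laboratory Manual updates. It adds no visit and, if the samples are adequate, no extra venepuncture. Investigators take on the review of the additional reports. A few more repeat tests or withdrawals are possible; the upper assumed case costs two percentage points of planned power.

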8.2.2.1 Phone Call Check-In (Weeks 1, 3, 5, 7, 9 and 11)

- Patients will receive a phone call 7 ± 2 days after each in-clinic visit (except after Week 12) to discuss any possible adverse events or other medical changes that may have occurred since their last visit
- Patients will also be asked about compliance to AP and Study Medication schedule

8.2.3 Safety Follow-Up Procedures (Week 13)

- Due to the COVID-19 pandemic and the possibility for site closures and/or travel restrictions, the Safety Follow-up visit may be conducted remotely via phone/audio or video conferencing platforms (with the exception of Facebook) per Investigator discretion.
 - Review of adverse events and concomitant medications including stable background AP therapy
 - Brief physical examination (if in-clinic visit)

9. SELECTION AND WITHDRAWAL OF PATIENTS

9.1. Inclusion Criteria

1. Patient should be able to read, understand and voluntarily sign an informed consent document prior to any study related assessments and procedures being conducted. Patients should be willing to comply with the study visits and requirements of the study protocol.
2. Patient should be between 18 and 55 years of age, inclusive, at the time of signing the informed consent document.
3. Physician confirmed DSM-V diagnosis of schizophrenia for the past 2 years based on patient's history and confirmed by psychiatric evaluation and MINI International Neuropsychiatric Interview Psychotic Disorders, version 7.0.2 (MINI, Version 7.0.2; see [APPENDIX L](#)).
4. The patient is an outpatient with no hospitalization for worsening of schizophrenia within 3 months of the first Screening Visit (Week -5).
5. Patients currently treated with one antipsychotic (AP) medication which has been unchanged (medication and dose) for at least 7 weeks prior to the first Screening Visit (Week -5), and expected to remain unchanged during the Screening and Treatment period. Allowed orally dosed APs are:
 - a. Aripiprazole
 - b. Asenapine
 - c. Brexipiprazole
 - d. Cariprazine
 - e. Lurasidone
 - f. Olanzapine
 - g. Paliperidone
 - h. Quetiapine
 - i. Risperidone

Note: If the patient is being treated with depot or long-acting antipsychotics, they should be on the treatment for at least 2 drug administration cycles prior to the first Screening Visit (Week -5).

6. Patients with confirmed blood levels of their current AP medication in samples drawn at the Qualification Visit (Week -3).
7. The patient has a reliable informant who is able to provide information regarding the patient and support study participation.

8. Patients with clinically stable schizophrenia with residual symptoms defined as PANSS total score of 70-110 per evaluation at the first Screening Visit (Week -5), the Qualification Visit (Week -3) and Day 1.

Note: At Week -3 and Day 1, the PANSS total score may vary by 10 points as compared to a previous visit, as long as total score remains between 70-110 at each of the three visits for the patient to be included in the study.

Patients must also meet these additional PANSS criteria:

- a. PANSS score of ≤ 4 on positive scale items of conceptual disorganization and hostility
- b. PANSS score ≥ 4 on **at least two** of the following items:
 - a. Delusions
 - b. Hallucinations
 - c. Suspiciousness/Persecution
 - d. Unusual thought content
- c. PANSS Negative Symptom Factor Score (NSFS) ≥ 12

9. If of reproductive age and not infertile (defined below), willing and able to use a medically highly effective form of birth control during the study and for 4 weeks following last dose of Study Medication. Examples of medically highly effective forms of birth control are:
 - a. Surgical sterility (via vasectomy, hysterectomy or bilateral ligation) or post-menopausal females (have had spontaneous amenorrhea for at least the last 1 year and at least 1 year after the onset of amenorrhea while not receiving hormone replacement therapy and have a Follicle-Stimulating Hormone (FSH) level greater than 40 mIU/mL)
 - b. Sexual partner is sterile, or of the same sex
 - c. Implants of levonorgestrel in females
 - d. Oral contraceptive (combined or progesterone only) in females
 - e. Double-barrier method (any combination of physical and chemical methods)
 - f. Intrauterine device in females, or other method with published data showing that the lowest expected failure rate is less than 1% per year
10. Healthy, as determined by the Investigator, based on a medical evaluation including history, physical examination, vital signs, electrocardiogram (ECGs) and clinical laboratory assessments at Week -5.

Note: A patient with a non-clinically significant abnormality or laboratory parameters outside the reference range may be included only if the Investigator considers that the finding will not compromise the patient's safety and will not interfere with the study procedures or data interpretation.

11. Body mass index (BMI) within the range of 18 to 40 kg/m², inclusive, at the first Screening Visit (Week -5).

